4.4 Demographic Data and Patient Characteristics

4.4.1 General Approach

All endpoints will be summarized on the safety analysis set, unless specified otherwise. Endpoints will be summarized by indication including an appropriate overall summary, unless specified otherwise. Each individual endpoint section also describes any further categorization of the data along with what is described in this section. Data from all core studies will be used in demographic and patient characteristics outputs.

4.4.2 Patient Disposition

Patient disposition will be summarized using standard summary statistics.

The following patient disposition items will be summarized by absolute counts (n) and percentages (%):

- Completed treatment period
- Discontinued from treatment period (including reason for discontinuation)
- Completed taper period
- Discontinued from taper period (including reason for discontinuation)

A further table split by site will be produced, showing number of patients enrolled, withdrawn and completed the treatment period at each site.

The number of patients who withdrew at any time and by each 12 week period (described in Section 4.5.9) will also be summarized by indication and core study.

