4 EXPERIMENTAL PLAN

4.1 Study Design

This is a multi-center, OLE study for patients with DS or LGS who have completed the double-blind, placebo-controlled, clinical studies of GWP42003-P (Core Studies). The study consists of a titration period and a maintenance period, followed by a 10-day taper period.

Titration Period: All patients will titrate up to 10–20 mg/kg/day GWP42003-P using a recommended titration schedule (see [APPENDIX 4](#)). It is advised that the Investigator considers monitoring hepatic function (alanine aminotransferase [ALT], aspartate aminotransferase [AST], total bilirubin [TBL] and international normalized ratio [INR] levels) during the titration period for patients taking concomitant AEDs that are known to be associated with hepatic injury or failure. To minimize any elevations in hepatic function markers the titration period can be extended and the dosage of a concomitant AED and/or GWP42003-P may be adjusted at the discretion of the Investigator. If there is intolerance during titration, the patient may be maintained on a dose below 10–20 mg/kg/day. A titration rate faster than recommended may be considered if there is an increase in seizures, following consultation with the GW medical monitor.

Maintenance Period: Patients will continue dosing at 10–20 mg/kg/day. However, Investigators may decrease the dose if the patient experiences intolerance, or increase the dose if required for better seizure control, until the optimal dose is found. The Investigator may schedule additional clinic visits to facilitate dose adjustments e.g., when increasing doses above 20 mg/kg/day. Patients whose dose has been decreased can have their dose increased again provided there is adequate tolerance. The maximum dose patients can receive will be 30 mg/kg/day (51 mg/kg/day is the maximum dose safely used in the USA EAP to date with a mean dose of 24 mg/kg/day [$n = 59$]). Dose increases above 20 mg/kg/day are recommended to be done slowly, with maximum increments of 2.5 mg/kg every 5–7 days. If seizure freedom is achieved with use of GWP42003-P during the study, the Investigator can consider reducing the dose of concomitant AEDs after consultation with the GW medical monitor.

Study Completion: The maximum duration of this OLE study will be 4 years (208 weeks after Visit 1).

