- A patient with at least 2 years' participation in the OLE (≥ 104 weeks after Visit 1) will complete the OLE phase when GWP42003-P is approved in their indication and is commercially available. Patients will complete an

unscheduled 'End of treatment' visit to transition from OLE to commercial product. The timing will vary per patient and is projected to begin in February 2019.

- A patient with less than 2 years' participation in the OLE when GWP42003-P is approved in their indication and is commercially available will continue the OLE phase until reaching a maximum of 2 years' (104 weeks after Visit 1) OLE treatment, at which point an unscheduled 'End of Treatment' visit will be conducted. The unscheduled 'End of Treatment' visit will be conducted no earlier than 730 days after Visit 1.
- A patient who does not continue treatment with GWP42003-P will commence the 10-day taper period (down-titrating 10% per day for 10 days) and complete an 'End of Taper Period' visit followed by a Follow-up visit (which can be by telephone) 4 weeks later.

Interim Analysis: At least one interim analysis will be conducted to support New Drug Application and Marketing Authorization Application filings. Further interim analyses may be conducted as required.

A study schema ([Figure 1-1](#)), presented at the end of [Section 1](#), depicts the overall study design. More detailed information on treatment and study procedures is provided in [Section 8](#) and [Section 9](#), respectively, and is summarized in [APPENDIX 1](#).

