3.1.3 Study Completion and Taper Period

If market authorization is granted for GWP42003-P (in DS or LGS) or after a maximum period of time receiving treatment, depending on the country in which the patient enrolls, (whichever occurs first), the patient will complete the study. Patients who do not immediately continue to use GWP42003-P will then commence a taper period (down-titrating 10% per day for 10 days) and complete an 'End of Taper Period' visit followed by a Follow-up visit (can be by telephone) four weeks later. If a patient opts not to continue with GWP42003-P treatment, they will commence the 10-day taper period and complete the 'End of Taper Period' visit and the Follow-up visit. If supported by the safety data, the Sponsor will look to extend the duration of this study.

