4. STATISTICAL METHODS

4.1 General Considerations

All tables will be presented by indication (where appropriate), including an overall count, as follows:

Dravet Syndrome (N=XX)	Lennox-Gastaut Syndrome (N=XX)	Overall (N=XX)
------------------------	--------------------------------	----------------

In all tables, listings and figures, the study visits will be referred to and labelled as per [Table 2](#)

Table 2 Study Visits

Actual Visit	Visit Label
Visit 1: Day 1	Day 1
Visit 2: Day 15	Day 15
Visit 3: Day 29	Day 29
Visit 4: Day 85	Day 85
Visit 5: Month 6 or Week 24	Week 24
Visit 6: Month 9 or Week 38	Week 38
Visit 7: Week 48 or End of Treatment (only patients who completed at 1 year)*	Week 48
Visit 8: Week 76	Week 76
End of Treatment (only patients who completed on or after Day 400)*	End of Treatment

End of Treatment (withdrawn patients only)	End of Treatment
End of Taper	End of Taper
Post-Taper Safety Call	Post-Taper Safety Call
Safety Follow-Up	Safety Follow-Up

* For some patients, the end of treatment visit occurs after one year in the OLE, whereas for other patients the end of treatment visit occurs after two or more years in the OLE.

Unless stated otherwise, continuous variables will be summarized showing the number of non-missing values (n), mean, standard deviation, median, minimum and maximum and categorical variables will be summarized showing the number and percentage of patients falling in each category. For continuous summaries of seizure frequency, the lower and upper quartiles will also be presented.

Minimum and maximum values will be presented to the same decimal precision as the raw data. Mean and median will be presented to one more decimal place than the raw data, and standard deviation to 2 more decimal places than the raw data. Percentages will be presented to one decimal place.

For patients who enter the OLE on the same day as the core study end of treatment or end of taper visit, the CRF for this study did not require some data to be entered for a second time. Hence, for visit based endpoints, if a patient does not have data entered in this study at Visit 1, then data from the end of treatment or end of taper visit in the core study will be used, provided that the date of collection is on Day 1 of the OLE.

Unless otherwise stated, all summaries will be presented by indication.

All analyses and summaries will be produced using SAS Version 9.4.

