Appendix 5 List of Tables, Listings and Figures

Lists of the tables, listings and figures to be provided are given below in [Table 12](#), [Table 13](#) respectively

Table 12 List of Tables

Table Number	Title	Analysis Set
Table 1.1	Summary of Patient Disposition – Numbers of Patients Enrolled, Withdrawn or Completed by Site	All Enrolled Patients
Table 1.2	Summary of Patient Disposition – Primary Reason for Withdrawals	All Enrolled Patients
Table 1.3	Summary of Withdrawals by Core Study and Visit	Safety Analysis Set
Table 2.1	Summary of Important Protocol Deviations	All Enrolled Patients
Table 2.2	Summary of Analysis Sets	All Enrolled Patients
Table 3.1	Summary of Demographic Data	Safety Analysis Set
Table 3.2	Summary of Baseline Characteristics	Safety Analysis Set
Table 5.1	Summary of Previous Significant Non-Epilepsy Medical or Surgical History Now Resolved	Safety Analysis Set
Table 5.2	Summary of Significant Non-Epilepsy Medical or Surgical History – Current Conditions	Safety Analysis Set
Table 6.1	Summary of Concomitant Antiepileptic Therapies	Safety Analysis Set
Table 6.2	Summary of Concomitant Antiepileptic Medications	Safety Analysis Set
Table 6.3	Summary of Concomitant Rescue Medications	Safety Analysis Set
Table 6.4	Summary of Other Concomitant Medications	Safety Analysis Set
Table 9.1.1.1	Summary of Total Seizure Frequency	Safety Analysis Set
Table 9.1.1.2	Summary of Total Seizure Frequency (LOCF)	Safety Analysis Set
Table 9.1.2.1	Summary of Drop Seizure Frequency	Safety Analysis Set
Table 9.1.2.2	Summary of Drop Seizure Frequency (LOCF)	Safety Analysis Set
Table 9.1.3.1	Summary of Convulsive Seizure Frequency	Safety Analysis Set
Table 9.1.3.2	Summary of Convulsive Seizure Frequency (LOCF)	Safety Analysis Set
Table 9.2	Summary of Patients with Status Epilepticus	Safety Analysis Set
Table 9.3.1	Summary of the Subject/Caregiver Global Impression of Change	Safety Analysis Set
Table 9.3.2	Summary of Subject/Caregiver Global Impression of Change in Seizure Duration	Safety Analysis Set
Table 9.4.1.1	Summary of Total Seizure Frequency - Patients Taking Clobazam	Safety Analysis Set
Table 9.4.1.2	Summary of Total Seizure Frequency - Patients Not Taking Clobazam	Safety Analysis Set
Table 9.4.2.1	Summary of Drop Seizure Frequency - Patients Taking Clobazam	Safety Analysis Set
Table 9.4.2.2	Summary of Drop Seizure Frequency - Patients Not Taking Clobazam	Safety Analysis Set

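### Withdrawals are summarised as counts per 12-week period with no number at risk, although planned treatment length is unequal, so late-period counts cannot be read as withdrawal risk

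*SAP*

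**What the plan says.** SAP 4.4.2 plans counts and percentages of patients who completed or discontinued the treatment period, with reasons for discontinuing. It then adds, for each indication and core study: "The number of patients who withdrew at any time and by each 12 week period (described in Section 4.5.9) will also be summarized". The matching output, Table 1.3 in SAP Appendix 5, is titled "Summary of Withdrawals by Core Study and Visit" and is run on the safety analysis set. Neither place gives a number at risk, a life table, a Kaplan-Meier estimate or a split by planned treatment length.

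Planned length is not the same for everyone:

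- SAP 3.1.3: a patient completes at market authorization or "after a maximum period of time receiving treatment, depending on the country in which the patient enrolls", whichever comes first.
- SAP 4.1, footnote to Table 2: "For some patients, the end of treatment visit occurs after one year in the OLE"; for others, "the end of treatment visit occurs after two or more years in the OLE".
- Protocol 4.1: one maximum of 208 weeks. Completion is earlier once the product is approved in the patient's indication and commercially available. For a patient with under two years in the study at that point, the end-of-treatment visit "will be conducted no earlier than 730 days after Visit 1".

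For adverse events by time of first onset, SAP 4.5.2 does use a period-specific base: patients with a visit or follow-up call in that period. No such rule is given for withdrawals.

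**The concern.** The primary objective is long-term safety and tolerability, and how many patients stop early, and when, bears directly on it. A patient who finishes as planned can no longer withdraw. If that patient stays in the denominator, later periods look quieter than they are, and tolerability can seem to improve when only the number under observation has fallen. Two groups with the same risk can also look different because one has more patients with a short planned course. Other outputs show little about late timing; the adverse-event onset table in SAP 4.5.2, for example, pools everything after Day 98.

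**Working it through.** The documents give no withdrawal or retention figure, so there is nothing to reproduce. What follows is an illustration.

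**Inputs from the documents.** Twelve-week periods (SAP 4.5.9); about 680 patients (protocol 13.1); planned completion after one year for some patients, which SAP Table 2 labels Week 48, and after two or more years for the rest.

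**Assumed inputs.** A constant withdrawal probability *h* of 2%, 3% or 5% per period. A share *f* of 20%, 40% or 60% completing as planned at Week 48 (end of period 4), with the rest followed to at least Week 96 (end of period 8).

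**Formulas for cumulative withdrawal by Week 96.**

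- At-risk (Kaplan-Meier): 1 − (1−h)^8
- Counts over number entered: f × [1 − (1−h)^4] + (1−f) × [1 − (1−h)^8]
- Gap: f × [(1−h)^4 − (1−h)^8]

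| h | At-risk estimate | Counts/N, f = 20% | f = 40% | f = 60% | Gap in points |
|---|---|---|---|---|---|
| 2% | 14.9% | 13.5% | 12.1% | 10.6% | 1.4 to 4.3 |
| 3% | 21.6% | 19.6% | 17.6% | 15.5% | 2.0 to 6.1 |
| 5% | 33.7% | 30.6% | 27.6% | 24.6% | 3.0 to 9.1 |

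For example, with h = 5% and f = 60% the gap is 0.6 × (0.8145 − 0.6634) = 9.1 points. It is zero when f = 0. Through Week 48 it is zero for any f: at h = 3% both methods give 11.5%.

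**Per-period view, N = 680, h = 3%, f = 40%.** The numbers at risk are 680, 660, 640 and 621 in periods 1 to 4, then 361, 350, 340 and 330. In period 4, 18.6 expected withdrawals over 680 is 2.7%. In period 5, 361 × 0.03 = 10.8, and 10.8/680 is 1.6%. The risk among those still under observation is 3.0% in both.

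**Two groups with identical risk (h = 3%).** With 20% and 60% short-course patients, counts over N give 19.6% and 15.5%; the at-risk estimate is 21.6% in both.

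**Protocol horizons alone.** The earliest planned completion, Day 730, falls in period 9 (Days 673 to 756), so cumulative counts to Week 96 would be unaffected and the problem starts later. Assume 15% withdraw per year, with half the patients completing at two years and half at four. Two-year risk is 1 − 0.85² = 27.75% and four-year risk is 1 − 0.85⁴ = 47.8%. The crude figure is 0.5 × 27.75 + 0.5 × 47.8 = 37.8%. With 20% or 80% completing at two years it is 43.8% or 31.8%.

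**The case against.** The strongest reply is that the plan does not produce the biased figure. The per-period sentence in SAP 4.4.2 promises a number of patients and states no percentage or denominator; no retention rate is defined anywhere. Completers are reported apart from discontinuations, so they are not called retained. A reader might infer that the plan overstates long-term retention. The documents do not support that as a flat statement: it holds only if counts are set against the number entered, and only after planned completions begin. A different reading errs the other way. In the example above, patients still on treatment at Week 96 over those entered is 0.6 × 0.97^8 = 47.0%, far below the true 78.4% retention. Even so, SAP 4.1 makes number and percentage under a column N the default and Table 1.3 names the safety analysis set, so entry N is the natural base. If only counts are printed, the reader has no base for late periods at all.

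A reader might also infer that comparisons between indications or core studies are confounded. That needs the mix of planned lengths to differ between them, and the documents do not give the mix. Nor do they say which country has which length: 3.1.3 mentions country without lengths, and the Table 2 footnote gives lengths without country. No formal comparison is planned. These limits stand.

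Other outputs help in part: discontinuations due to adverse events are tabulated (Tables 12.3 and 12.4), dosing days are summarised, and disposition and visit dates are listed. None gives withdrawal risk over time. The number of patients in the seizure tables is no substitute, because it depends on diary calls and excludes GWEP1332 Part A.

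**Conclusion.** The point holds in a limited form. Follow-up is unequal by design under the SAP and under the protocol alone, and the withdrawal summary takes no account of it. After the first planned completions, counts set against entry N understate withdrawal risk; before then there is no bias. Distortion between indications or core studies is a possibility, not a finding.

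The size is unknown. The 1.4 to 9.1 points at Week 96 rest on assumed withdrawal of 2% to 5% per period, constant over time, and on 20% to 60% of patients completing at Week 48. They also rest on the SAP's one-year completion, which protocol 4.1 does not contain. Under the protocol's horizons the effect starts only after Day 730, and its size again depends on assumed rates. No hypothesis test or planned endpoint is invalidated. What is affected is how the late part of a long-term tolerability study can be read.

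**What to change.** In SAP 4.4.2 and Table 1.3:

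1. Show the number at risk at the start of each 12-week period and use it as the percentage base for that period's withdrawals.
2. Add a Kaplan-Meier estimate of time to withdrawal from Day 1, with 95% confidence intervals, by indication. Censor at by-design completion or transition to commercial product. This assumes that patients with short planned courses would otherwise have withdrawn at the same rate as those followed longer, and the SAP should say so.
3. Align the Table 1.3 title, which refers to visits, with the 12-week periods in the text.
4. Reconcile the SAP's one-year and country-dependent completion (3.1.3 and Table 2) with protocol 4.1, so that the censoring date is defined for every patient.

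Cumulative incidence of withdrawal due to an adverse event, with other withdrawals as competing events, and a split by core-study treatment are useful but optional.

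The cost is a few sentences and one extra table or figure, from disposition and visit dates already planned for Listings 1.1.1 and 1.3. The downside is that the stated long-term withdrawal may be higher.

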4.4.3 Analysis Sets

Patients included in the safety analysis set, and patients excluded together with reasons for exclusion, will be summarized by absolute counts (n) and percentages (%).

The number of patients included in the safety analysis set from each core study will also be presented.

4.4.4 Demographic Data and Baseline Characteristics

The following demographic data will be summarized:

- Age (years);
- Age group (2-5 years, 6-11 years, 12-17 years and 18-55 years);
- Sex;
- Race;
- Country;
- Region (US, Rest of the World);
- Weight at Visit 1 (kg);
- Height at Visit 1 (cm);
- Body mass index at Visit 1 (kg/m²).

Age will be calculated as:

$$(\text{Date of Visit 1} - \text{date of birth}) \div 365.25$$

The following baseline characteristics will be summarized by indication and overall:

- Number of AEDs a patient is currently taking.
- Number of patients taking clobazam (Yes, No).
- Number of patients taking valproic acid (Yes, No).
- Number of patients taking lamotrigine (Yes, No).
- Number of patients taking levetiracetam (Yes, No).
- Number of patients taking rufinamide (Yes, No).
- Number of patients taking topiramate (Yes, No).
- Number of patients taking felbamate (Yes, No).

The number of AEDs a patient is currently taking is based on the 'Concomitant antiepileptic medications' CRF page. Patients taking the same AED type, but where the AED were coded to different generic terms will be counted only once within the AED type. For example, valproate sodium, valproic acid, valproate semisodium and ergenyl chrono will all be counted as valproic acid and counted once under that term.

4.4.5 Medical and Surgical History and Current Medical Conditions

All conditions and diagnoses on the 'non-epilepsy medical history' CRF page will be coded using Version 17.1 of the Medical Dictionary for Regulatory Activities (MedDRA).

The number of patients with relevant or significant non-epilepsy medical or surgical history and medical history by system organ class, and preferred term, will be summarized by absolute counts (n) and percentages (%). Percentages will be calculated based on the number of patients in the specific indication.

4.5 Safety and Efficacy Analysis

The safety of GWP42003-P is the primary endpoint and the aim of this study is to evaluate long term safety and tolerability and as such, there will be no formal hypothesis testing. Endpoints will be summarized as detailed in the following sections.

4.5.1 General Approach

All endpoints will be summarized on the safety analysis set, unless specified otherwise. Endpoints will be summarized by indication including an appropriate overall summary, unless specified otherwise. Each individual endpoint section also describes any further categorization of the data above that described in this section.

Throughout this section, whenever change from baseline is referenced and the endpoint is non-seizure related the baseline that is used will be the core study baseline. Please refer to Section 4.5.9 for specific rules for the choice of baseline for seizure-related endpoints.

